Discuss the research design including but not limited to such issues as: probability of group assignment, potential for subject to be randomized to placebo group, use of control subjects, etc.

STUDY PARTICIPANTS: parallel two-group design will be used to evaluate the intervention among n=150 young adults randomly assigned to the peer support intervention or usual care (1:1). Participants will be enrolled prior to or at their anticipated final visit in pediatric care at TCH and will be followed for 12 months after leaving pediatrics.

ADVISORY BOARD MEMBERS: There will be no group assignments or controls. Participants will not receive any treatment or intervention. By agreeing to be an advisory board member, participants are agreeing to be contacted about advisory questions that arise in the lab - they are not required to respond to any question, but rather will have the option to agree to answer at any time that they choose.

SUPPLEMENT ACTIVITIES PARTICIPANTS: A subset of up to 35 young adult participants will be asked to enroll to complete the additional follow-up data collection after they have completed the 12-month follow-up for the DiaBetter Together trial. We will enroll participants who completed the control and treatment arms of the initial trial.

Inclusion Criteria:

Young adult participant inclusion criteria: 1) has a diagnosis of type 1 diabetes of at least 1 year; 2) currently receiving care at a TCH Diabetes Care Center location; 3) is between the ages of 17-25 years at enrollment; 4) exhibits fluency in reading/speaking English; & 5) their endocrine provider confirmed plans to transfer to an adult provider within 3-6 months of the upcoming diabetes care appointment.

Peer Mentor participant inclusion criteria: 1) was diagnosed with type 1 diabetes before age 18; 2) has a diagnosis of type 1 diabetes of at least 1 year; 3) is between the ages of 20-35 at enrollment; 4) has been previously treated in pediatric care and is currently treated in adult care; 4) demonstrated interest and ability to effectively deliver the peer intervention & 5) exhibits fluency in reading/speaking English

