As a supplement to HbA1c, we will also collect continuous glucose data, as recommended by recent consensus guidelines to measure glycemic control with measures beyond HbA1c. We will collect these data directly from participants who are using a continuous glucose monitor (CGM) device. We will collect 14 days of raw data and summary variables (e.g., estimated average glucose, percent time in target glucose range) using cloud-based data platforms either from the manufacturer (e.g., Dexcom Clarity) or using the Texas Children's Hospital healthcare professional access (e.g., Glooko). To use manufacturer platforms, participants will be asked to follow the platform's process to grant data access to study staff via a 12-month code. This is the same process patients use to share CGM data with clinical providers as part of usual care. We will collect data at the same timepoints we are collecting other glycemic control data: baseline and 12 months. We will not collect glucose data for any participant not currently using CGM.

Randomization Participants will be randomized upon completion of baseline questionnaires and return of a completed home A1c kit to intervention or usual care in a 1:1 ratio using a permuted block design. The intervention will begin that day and take place for 12 months.

Peer Mentor Recruitment Peer Mentors will deliver the intervention and will also be enrolled as study participants to permit assessment of their own outcomes. Peer Mentors will be experienced young adults with T1D who have transferred to adult diabetes care. Potential Peer Mentors will be recruited through referrals from previous pediatric providers at TCH, via advertisements in local adult diabetes care centers including BCM (with the support of [name], Co-I), local chapters of the College Diabetes Network, local diabetes group newsletters, and social media. Interested Peer Mentors will be screened for eligibility and interest. Peer Mentors will provide informed consent prior to completing questionnaires and being trained.

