Data Analysis Plan. Baseline demographics and clinical characteristics will be summarized by means with standard deviations, medians with minimum and maximum values, or frequencies with percentages. Summary statistics will be stratified by treatment arm and compared between groups using two-sample t-tests, Wilcoxon rank sum tests, or Fisher's exact tests. Approximate normality for continuous measures will be assessed using quantile-quantile plots and Shapiro-Wilks tests. Departures from normality will be addressed by data transformation (e.g., natural logarithm), categorization, or non-parametric analysis. Statistical significance for the univariable analysis will be assessed at the two-sided 0.05 level; however, significant differences between treatment arms must be due to chance since this is a randomized clinical trial. Missing data on questionnaires are expected to be minimal based on high follow-up data completion rates in preliminary intervention studies and <1% missing item responses in our preliminary study with a similarly-aged sample of young adults. Measures will be scored according to published instructions including rules for handling missing item responses. SAS v9.4 (Cary, NC) will be used for all data summaries and analysis. Aim 1: The primary outcome measure of interest is 12-month HbA1c. An independent, two-sample t-test will be used to compare mean HbA1c between study arms at the 12-month time point. An F test will be used to test the null hypothesis that the variances are equal, and approximate normality will be assessed using QQ-plots and the Shapiro Wilks test. Departures from model assumptions will be addressed by data transformations (e.g., natural logarithm), categorization, or alternative methods of analysis such as Welch's t-test approximation or the Wilcoxon rank sum test. Statistical significance will be assessed at the 0.05 level (2-sided). A general linear mixed model will be used to compare mean HbA1c between study arms after adjusting for baseline HbA1c and other clinically relevant covariates. Parameter estimates for the regression model will be assessed at the 0.05 level of significance (2-sided). Secondary outcomes include the time to first adult care visit, treatment adherence, and quality of life. The time to first adult care visit will be compared between treatment arms using the log-rank test statistic for comparing Kaplan-Meier curves. Time will start on the date of the last pediatric care visit. The event of interest is the date of the first adult care visit. Participants who do not follow-up with an adult care provider within 12 months of the last pediatric visit will be censored for the event at the 12-month time point. The log-rank test statistic will be assessed at the two-sided 0.05 level of significance. A Cox Proportional Hazards

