
regression model will also be used to estimate the Hazards Ratio (95% confidence interval) for adult care follow-up in the intervention versus control groups. Treatment adherence and quality of life will be analyzed using separate general linear mixed models to compare means between study arms over time. The models will include fixed effects for baseline measure, time (6 vs. 12 months), study arm, and the time-arm interaction term. Adherence and quality of life will be analyzed by separate models. Each model will be used to simultaneously compare mean adherence and quality of life measures at the 6- and 12-month time points adjusting for baseline values. Statistical significance will be assessed at the 0.05 level for all secondary hypothesis tests. Aim 2: Regression analysis will be used to test for mediation between study arm and the primary (HbA1c) and secondary outcomes (time to first adult care visit, adherence, quality of life) at 12 months. The 4-step approach recommended by Baron and Kenny¹⁰⁵ will be used to assess transition readiness, perceived support, diabetes strengths, diabetes distress, and depressive symptoms at 6 months as mediators for each outcome. Indirect effects will be assessed by computing the difference between two regression coefficients^{106,107}. Standard errors will be estimated using Bootstrapping. Aim 3: Changes in Peer Mentors' self-report outcome measures will be assessed using paired t-tests or the Wilcoxon signed rank test. Statistical significance will be assessed at the 0.05 level of significance (2-sided). General linear mixed models may also be used to test the association between changes in measures over time with demographic and clinical characteristics. The models will include time (baseline vs. follow-up), covariates, and the covariate-time interaction term. The matrix of correlated residuals will assume an unstructured format.

SUPPLEMENT ACTIVITIES DATA ANALYSIS: We will conduct descriptive statistics (means with standard deviations, medians with minimum and maximum values, or frequencies with percentages) and basic correlations between variables of interest. We will use NVivo software to code qualitative transcripts and conduct hybrid thematic analysis.

Section H: Potential Risks/Discomforts

H1. Potential Risks/Discomforts

Describe and assess any potential risks/discomforts; (physical, psychological, social, legal, or other) and assess the likelihood and seriousness of such risks:

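### Aim 2 treats 6-month scores as mediators of time to first adult care visit, although that visit can come before the score and the visible plan has no rule for this

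*Combined protocol and SAP*

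**What the plan says.** Section G2, Aim 2, looks for mediation between study arm and the primary outcome, and also "secondary outcomes (time to first adult care visit, adherence, quality of life) at 12 months". The candidate mediators are transition readiness, perceived support, diabetes strengths, "diabetes distress, and depressive symptoms at 6 months as mediators for each outcome". The method is the Baron and Kenny four-step approach; "Indirect effects will be assessed by computing the difference between two regression coefficients", with bootstrap standard errors. Aim 2 does not name the regression model for the visit outcome. Under Aim 1 the only regression named for it is a Cox model.

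The visit outcome is defined under Aim 1: "Time will start on the date of the last pediatric care visit". The event is the first adult visit, and participants without one are censored at 12 months. No earliest event date is set.

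Three other places bear on timing:

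- F1, inclusion criteria: the endocrine provider has "confirmed plans to transfer to an adult provider within 3-6 months of the upcoming diabetes care appointment".
- F1, design: "Participants will be enrolled prior to or at their anticipated final visit in pediatric care at TCH", and they "will be followed for 12 months after leaving pediatrics".
- F2, randomization: "Participants will be randomized upon completion of baseline questionnaires and return of a completed home A1c kit". The 12-month intervention starts that same day.

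F2 mentions a 6-month time point, says it is described further on, and then continues in a Section S attachment that is not in the file.

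**The concern.** A mediator has to come before the outcome it explains. Here the outcome is a date that can fall anywhere in the 12 months after the last pediatric visit, while the mediator is fixed at one questionnaire. For a participant already seen in adult care when the questionnaire is completed, the order is reversed. Readiness, perceived support and distress could each plausibly change because an adult visit has taken place. A score that the visit changed could then be reported as the mechanism that produced the visit. Limiting the outcome to 12 months does not help, because visit time or status by month 12 still includes the early visits. What is at stake is the mechanistic claim for one outcome of an explanatory aim.

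**Working it through.** **The plan's own figure.** The plan gives no figure for Aim 2. Its 64 per group for HbA1c reproduces: difference 0.5, SD 1, two-sided 0.05 and 80% power (power is not stated, so assumed) give 63.77 by the t-test, rounded up to 64. I use 2 x 64 = 128 as the analysis size below.

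**Timing.** Let s be the months from the last pediatric visit to the 6-month score.

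- Clock from leaving pediatrics, or from randomization at the final pediatric visit: s is about 6. It is 7 if kit return delays randomization by a month.
- Clock from randomization 3 months before the final visit: s = 3.
- Clock from randomization 6 months before it: s = 0.

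A visit at time T precedes the score whenever T < s. Since T starts at the last pediatric visit, this is ruled out for everyone only if s is 0 or less.

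**Share of controls seen before the score.** Assumed cumulative hazard H(t) = L(t/12)^k, with L = 1.2 or 2.4. The 12-month totals are 1 - exp(-1.2) = 69.9% and 1 - exp(-2.4) = 90.9%. The hazard is constant (k = 1) or rising (k = 2). The share is 1 - exp(-L(s/12)^k); for example, L = 1.2, k = 1, s = 6 gives 1 - exp(-0.6) = 45.1%.

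| s | k=1, L=1.2 | k=1, L=2.4 | k=2, L=1.2 | k=2, L=2.4 |
|---|---|---|---|---|
| 7 | 50.3% | 75.3% | 33.5% | 55.8% |
| 6 | 45.1% | 69.9% | 25.9% | 45.1% |
| 3 | 25.9% | 45.1% | 7.2% | 13.9% |
| 0 | 0 | 0 | 0 | 0 |

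As a share of all 12-month visits, s = 6 gives 37%-77% (25.9/69.9 to 69.9/90.9) and s = 3 gives 10%-50%.

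**False mediation claims.** Simulation with 64 per arm, arm hazard ratio 1.5 or 2.0, Cox model (assumed) censored at 12 months, 2000 replicates and 200 resamples. Score = a x arm + d x (visit before s) + standard normal noise, and visit time does not depend on that noise, so there is no true mediation. The bootstrap rule is |c - c'| > 1.96 bootstrap SE, where c and c' are the arm coefficients without and with the score. The documents do not list the four steps. I took arm-outcome, arm-score and score-outcome given arm each at p < 0.05, with |c'| < |c|. Ranges are over the eight combinations of k, L and hazard ratio.

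| a, d (SD) | s | Bootstrap alone | Four steps plus bootstrap | Four steps alone |
|---|---|---|---|---|
| 0.5, 0.5 | 6 | 7.9%-21.6% | 4.2%-19.8% | 16.4%-48.5% |
| 0.5, 0.5 | 3 | 1.2%-16.1% | 0.7%-15.0% | 3.8%-46.0% |
| 0.5, 0.5 | 0 | 0.5%-0.8% | 0.1%-0.4% | 0.8%-2.4% |
| 0.5, 0.25 | 6 | 2.0%-4.8% | not run | 5.1%-15.0% |
| 0.5, 0.25 | 3 | 0.6%-3.6% | not run | 1.8%-13.8% |

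With d = 0 the bootstrap rate is 0.5%-1.1%. With a = 0 and d = 0.5 it is 0.1%-1.3%.

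**Landmark check.** Among participants with no visit before s, the score coefficient is significant in 4.7%-6.4% of trials, close to nominal. The number left at s = 6 runs from 64 x (exp(-1.2) + exp(-2.4)) = 25 (L = 2.4, k = 1, hazard ratio 2.0) to 64 x (exp(-0.3) + exp(-0.45)) = 88 (L = 1.2, k = 2, hazard ratio 1.5). At s = 3 the same formula gives 54-117.

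**The case against.** The best defense has four parts.

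- **The questionnaire clock may favor the plan.** F2 collects participants' reports on their mentors at 6 months, and the Section R advertisement describes three questionnaires over one year. Both fit a clock from randomization, which may precede the last pediatric visit. If transfer means leaving pediatrics, the score then leads and few visits come before it. This stands as a limit on size, and a shared origin is close to the late end. It does not remove the problem: at a 3-month lead, 7%-45% of controls are still seen first.
- **A reader might infer that the plan fails to date the 6 months.** The documents do not support that. The date may be in the F2 attachment, which was not supplied.
- **A reader might infer false claims in up to half of trials.** The 16%-49% range is for the four steps alone, and the plan also bootstraps the indirect effect. The higher bootstrap rates need 0.5 SD effects of both arm and visit on the score, and the documents give neither. In a smaller check at a shared origin, an arm effect of 0.25 SD with a visit effect of 0.5 SD gave 3.5%-6.5%. In a second simulation in which the arm had no direct effect on the score, the mean coefficient difference was near 0 (0.000 to 0.003 with a visit effect), although the score-outcome step was falsely significant in 23%-70% of trials with visit effects of 0.3-0.5 SD.
- **A reader might infer that a Cox coefficient difference itself creates false mediation.** Aim 2 names no Cox model. If one is used, adding a prognostic score without mediation moves the difference by -0.04 to -0.16 (0.5 or 0.7 log hazard per SD; -0.011 to -0.022 at 0.2). That enlarges the arm coefficient, the opposite of the harm described here.

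**Conclusion.** The concern holds for time to first adult visit. As written, Aim 2 allows a score measured after the visit to be treated as its mediator, and no visible rule prevents it. Taking first adult visits to follow the last pediatric visit, the problem is certainly absent only if the 6-month questionnaire is completed on or before the last pediatric visit.

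Its size is uncertain because the visit rate, the hazard shape, the clock origin and the effects on the score are all assumptions. Between 0 and 70% of controls are seen before the score across leads of 6 months to none. At a shared origin, false claims by the bootstrapped difference range from about 1%, if the arm or the visit does not move the score, through 2%-5% to 8%-22%.

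A reader might extend the criticism to all of Aim 2 or to the main results. The text does not support that: HbA1c, adherence and quality of life at 12 months follow the 6-month score, and neither the primary HbA1c comparison nor the log-rank test uses a mediator. The point is worth correcting in the analysis plan, but it bears on one explanatory analysis.

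**What to change.** Remove time to first adult visit from the 6-month mediator analysis. Keep the planned mediation analyses for 12-month HbA1c, adherence and quality of life.

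If the sponsor wants to keep the visit outcome, make it an exploratory landmark analysis. Include participants with no adult visit before the date they completed the 6-month questionnaire, start the clock at that date, and report the association of the score with later visits. Do not present a difference of coefficients as an indirect effect.

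The inclusion test is whether the completed questionnaire precedes the first adult visit. Fixing only the date from which the questionnaire is timed is not enough: timing it from the last pediatric visit gives s = 6, where 26%-70% of controls are already seen.

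The cost is analysis-plan wording, plus a little programming for the landmark. The downside is that mediation of the visit outcome is lost, or rests on a smaller subset that is no longer a randomized comparison: under the assumed rates, about 25-88 of 128 with a shared origin and 54-117 with a 3-month lead.
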